2.4 Known Potential Risks

The application of mechanical thromboprophylaxis is a standard practice in many populations and is not considered to pose serious health risk. The risks include mild discomfort, interference with sleep and movement, injury due to falling, skin breakdown ulceration, and worsening of leg ischemia in patients with peripheral arterial disease. Risks of serious events including peripheral nerve palsy, circulatory compromise such as limb ischemia, deep vein thrombosis, pulmonary embolism, pressure ulcers (NPUAP category III and IV), and neuropathy is exceedingly rare but may occur as a result of use of intermittent pneumatic compression. Subjects who are at higher risk of such complications (subjects with pre-existing severe peripheral vascular disease or severe edema of lower extremities) will be excluded from the study. Adverse events of special interests are outlined in section [10.1.4](#)

Additional adverse events expected in the target population include, but are not limited to, infection, bleeding, delirium, thrombosis, shock, respiratory failure, kidney injury, liver injury, and death.

All subjects will be monitored for adverse events over the course of the intervention as outlined in Section [10](#).

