3 STUDY OBJECTIVES

3.1 Primary Objective

Part 1: To determine the tolerability of the OsciPulse device on healthy individuals.

Part 2: To assess the safety and tolerability of the OsciPulse device compared to a standard intermittent pneumatic compression device.

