4 STUDY PLAN

4.1 Study Design

This is a single site, two-part study. Part 1 is in healthy subjects testing the tolerability of the device. Part 2 is a Phase 2, randomized crossover study in subjects with the potential to develop VTE evaluating the OsciPulse device compared to a standard intermittent pneumatic compression device. Our hypothesis is that the safety and tolerability of the OsciPulse device is equivalent to the standard compression device.

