4.6 Study Endpoints

4.6.1 Primary Study Endpoints

The primary endpoint will be subject safety and tolerability. Safety will be evaluated by the presence of adverse events (See section 10) during the intervention. Tolerability will be evaluated by a subject reported questionnaire. Tolerability will be measured by the 100-mm visual analog scale (VAS) and through open ended question answers. The average distance on the VAS in each domain of the questionnaire will be compared between the OsciPulse device and standard IPC.

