9 STATISTICAL PLAN

9.1 Part 1

Part 1 of the trial is designed to test the tolerability of the OsciPulse system on healthy subjects for 3 hours prior to the 6-hour trial on patients. This is to determine if there are any immediate comfort issues that can be addressed prior to use in the clinical setting. Healthy volunteers are not the target population for the OsciPulse device and will have different tolerability for discomfort than hospital patients, but we feel that this test will be a qualitative analysis of the product prior to use in the target population. Subjects will indicate if the device caused 1) no discomfort, 2) mild discomfort, or 3) significant discomfort. **We will require that all three subjects indicate that there was not “significant discomfort” as reported on the subject questionnaire before continuing to Part 2.** This will be confirmed by the monitor prior to continuation to Part 2.

9.2 Part 2

Part 2 of the trial is designed to assess the tolerability and hemodynamic efficacy of the OsciPulse device in the clinical setting. The Primary endpoint is tolerability, which will be evaluated with questionnaires scored with a visual analog scale and will be directly compared between the OsciPulse device and a reference therapy device. Evaluable subjects will have completed the 6-hour study time that includes 3 hours with both therapies. This allows for the comparison between the therapies that makes the data quantitative rather than subjective. We will further measure hemodynamic efficacy through vascular ultrasound measurements of venous flow

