9.2.1 Primary Endpoint

The primary endpoint of this study is OsciPulse device tolerability compared to the current standard of care device. This endpoint will be measured by quantifying the differences in the responses to the questions on the subject questionnaire for each device. We will compare the visual analog scale ratings for the first 4 questions for each subject between the OsciPulse device and the reference therapy device. There are also 4 questions on the 6-hour questionnaire that ask the participants to directly compare the two devices, to determine the difference in tolerability. The ratings are reported in millimeters and the average differences between the responses will be statistically evaluated using a paired t-test.

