9.2.2 Secondary Endpoints

The secondary endpoints of this study are the hemodynamic effects of each device on venous return dynamics. The hemodynamic endpoints will result from vascular ultrasound measurements

These hemodynamic parameters will be averaged across subjects and the difference between the measurements for each device will be evaluated using a paired t-test. The hemodynamic data will demonstrate the efficacy of the OsciPulse device to create the desired valve sinus reversing flow profile that has been shown in previous clinical studies with healthy volunteers. Confirming this flow in the subject population will demonstrate that the OsciPulse device can be successfully deployed in the clinical setting by clinical staff.

Safety will be monitored by tracking all adverse events during the 3-hour period of wearing each device and evaluated by determining the total number of events under each condition.

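### Safety is part of the primary endpoint in 4.6.1 but has no clear rank in section 9, where its only summary is a raw event total

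*Combined protocol and SAP*

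**What the plan says.** **Rank of safety.** The Part 2 primary objective in 3.1 is "To assess the safety and tolerability of the OsciPulse device compared to a standard intermittent pneumatic compression device". Section 4.1 states: "Our hypothesis is that the safety and tolerability of the OsciPulse device is equivalent to the standard compression device". Section 4.6.1 states: "The primary endpoint will be subject safety and tolerability". The statistical plan differs. Section 9.2 says "The Primary endpoint is tolerability", and 9.2.1 says "The primary endpoint of this study is OsciPulse device tolerability compared to the current standard of care device". Section 9.2.2 is headed Secondary Endpoints and defines these as hemodynamic effects. It then closes with a sentence on safety, without saying which rank safety holds.

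**Measure of safety.** Section 4.6.1 says "Safety will be evaluated by the presence of adverse events". Section 9.2.2 says safety will be "evaluated by determining the total number of events under each condition". Section 9.2.4 gives paired t-tests for the visual analog ratings and venous flow and no method for adverse events. Section 9.2.7 provides for adverse event information on every randomized subject but names no summary measure.

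**Who is counted.** Section 9.2.7 covers all randomized subjects. Section 9.3 defines one population of protocol-compliant completers, leaves everyone else out of the analysis, and makes no exception for safety.

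**The concern.** The title, objectives and hypothesis promise a safety conclusion, yet a reader of section 9 cannot tell whether safety is a primary result. The two descriptions of the measure are also not the same quantity. Presence is most naturally read as whether a subject had an event; a total counts every event.

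The difference matters in this population. Section 2.4 expects "infection, bleeding, delirium, thrombosis, shock, respiratory failure, kidney injury, liver injury, and death", and several of these can arise together from one illness. Section 10.1.1 defines an adverse event broadly, to include worsening of existing conditions and qualifying laboratory abnormalities. With few subjects and short exposure, totals will probably be small, so one subject's cluster can make up most of a device's total. Device use is unblinded (6.6). If the measure is left open, the headline figure could be chosen after the data are seen.

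**Working it through.** **1. The plan's own figure.** Section 9.2.3 allows for up to 6 of 20 subjects to be lost and expects 14 with evaluable tolerability and safety data: 20 − 6 = 14, which reproduces. The documents give no event rate, margin, alpha or power for safety, so no other stated figure can be checked.

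**2. The two measures.** Let e(i,d) be the number of adverse events in subject i that start on device d.

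- Total events: T(d) = sum over i of e(i,d).
- Subjects with an event: S(d) = number of i with e(i,d) ≥ 1.

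One subject adds at most 1 to S(d) but adds e(i,d), which has no upper limit, to T(d). The two measures can therefore rank the devices differently.

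**3. Illustrations (event patterns assumed; X and Y are the two devices).**

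| Pattern | Events X v Y | Subjects X v Y |
|---|---|---|
| One subject with 3 linked events on X; one mild event in one other subject on X; one mild event in one subject on Y | 3 + 1 = 4 v 1 | 2 v 1 |
| One subject with 3 linked events on X; one mild event in each of two subjects on Y | 3 v 1 + 1 = 2 | 1 v 2 |
| Two subjects with 1 and 5 events on X; one event in each of four subjects on Y | 1 + 5 = 6 v 4 | 2 v 4 |

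In the first row the cluster inflates the difference. In the second and third rows the direction reverses.

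**4. How often this could happen (simulation, all rates assumed).** There were 20,000 simulated trials per setting, with 14, 15 or 20 subjects and no true device difference. In each period 10% or 20% of subjects had a single event. In addition, 2%, 5% or 10% of subjects deteriorated in one randomly chosen period, with a mean of 4 or 6 clustered events. The two measures pointed in opposite directions in about 3% to 19% of trials across these settings.

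**5. Loss of pairing.** Take 15 subjects and totals of 2 v 2. These can come from two subjects with one event on each device (both 2, neither 13). They can also come from four different subjects (X only 2, Y only 2, neither 11). The first suggests subjects prone to events whatever the device; the second does not. The totals are the same.

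**6. Effect of the analysis set.** Take the second row of the table and suppose the subject with 3 events does not finish. Under 9.2.7 the totals are 3 v 2. Under 9.3 that subject is left out, and they become 0 v 2. The direction turns on which section is followed. The losses that 9.2.3 allows for include loss of consciousness and death, so the subjects whom 9.3 removes can be those with the most serious events.

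**The case against.** **The unit in 4.6.1 is inferred.** A reader might conclude that 4.6.1 fixes the subject as the unit and that 9.2.2 changes it. Section 4.6.1 does not say per subject, and 10.2 uses similar wording simply for what the record screen looks for. On that reading 4.6.1 says what is sought and 9.2.2 says how it is totalled. This stands: the measure is inconsistent on the natural reading and underspecified on the other.

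**Section 9.2.2 does not call safety secondary.** The sentence only falls under that heading. This also stands, but it leaves safety without a rank in section 9, which still conflicts with 4.6.1.

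**No inference rests on the total.** A reader might infer that one deteriorating patient could decide the device comparison, and might attach a p-value. Six events in one subject and none elsewhere would give a naive two-sided binomial p = 2 × 0.5^6 = 0.031, against 1 v 0 subjects and an exact McNemar p of 1.0. The documents do not support that reading: they state no safety test, margin or decision rule, and 10.5 has no stopping rules. What remains is the size and direction of a descriptive comparison.

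**A cluster would be visible.** Severity (10.2.1), relatedness (10.2.2) and events of special interest (10.1.4) are recorded, and complications of a serious event are reported as follow-up to it (10.4.1). That helps interpretation. However, the follow-up rule concerns reporting of serious events only, it is not tied to the 9.2.2 count, and none of these items settles which figure is the headline.

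**Presence is also crude.** In the second row of the table it ranks two mild events as worse than one serious deterioration. This is fair, and it is why severity and relatedness belong beside the main table.

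**Conclusion.** The point holds as an internal inconsistency in a stated primary endpoint. Safety is primary in 3.1, 4.1 and 4.6.1, is absent from the primary endpoint in 9.2 and 9.2.1, and is summarized in section 9 only by a raw total under the secondary heading. That conflict needs no assumption.

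The consequence is descriptive. One inpatient with several linked events can set the size and direction of the totals (3 v 2 events against 1 v 2 subjects in the assumed example), and a total ignores the within-subject pairing. How often the two measures would disagree depends on event rates that the documents do not give; the 3% to 19% range rests wholly on the assumed ones. The conflict between 9.2.7 and 9.3 compounds the problem, because it can remove the deteriorating subject altogether. The correction should be made, and it is cheap.

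**What to change.** - Give safety one rank in 4.6.1, 9.2, 9.2.1 and 9.2.2, in line with the primary objective in 3.1. Ranking it below tolerability throughout would also be consistent, but would mean rewriting the objective and hypothesis.
- Make the main safety summary the number of subjects with at least one adverse event starting on each device, shown as a paired table: both devices, OsciPulse only, IPC only, neither.
- Show total events, severity, relatedness and events of special interest alongside as supportive tables.
- Reconcile 9.2.7 with 9.3, so that a randomized subject who deteriorates and does not finish stays in the safety summary.

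The cost is protocol wording and one small table from data already collected. The downside is that repeat events in one subject appear only in the supportive tables. Separately, and of minor weight, wear time is a secondary endpoint in 4.6.2 but is missing from 9.2.2; it can be restored in the same edit.

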9.2.3 Sample Size and Power Determination

This study is a Phase 2 trial aimed at determining the tolerability and safety of an external device so we will use a convenience sample size of up to 20 enrolled subjects. This was determined in part by allowing that within our targeted population up to 6 subjects could experience an event during the 6-hour study window (discharge, unexpected surgery, loss of consciousness, death), and we would still have 14 subjects with evaluable tolerability and safety data.

9.2.4 Statistical Methods

The statistical approach to analysis will be to use paired t-tests to evaluate the difference between the standard of care cleared intermittent pneumatic device and the OsciPulse device using a

paired t-test. We will evaluate the primary endpoint of tolerability through quantification of the difference between the visual analog scale markings on the patient questionnaire for each device. We will also use a paired t-test to evaluate the changes in venous flow that occur in each patient during use of both devices.

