Statistical Methodology	Part1: Device tolerability will be assessed with a questionnaire focused on the comfort of the OsciPulse device. This data will only be used to validate the tolerability of the device for use in Phase 2 so no statistical analysis will be performed. Part 2: Device tolerability will be measured with a subject questionnaire focused on their comfort for both the OsciPulse device and the intermittent pneumatic compression device. The questions will have continuous visual analog scales to gauge responses, and we will use a paired t-test to evaluate the difference in responses between the OsciPulse device and the reference therapy. We will also monitor subject compliance, and venous valve sinus hemodynamics, when feasible, for each device and a paired t test will be used to compare those values.
Safety Evaluations	Part 1: Adverse events will be collected

Part 2: Adverse events will be collected. Expected AEs in this population include VTE, skin ulceration, peripheral nerve palsy, limb ischemia, and falls.

**Data and Safety
Monitoring Plan**

The Sponsor is responsible for monitoring the data quality and the ongoing safety of subjects.

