4.2.2 Study Intervention Phase

Part 1: Enrolled healthy subjects will have the OsciPulse device applied by study or medical personnel according to the OsciPulse Instructions for Use. The subject will wear the device for a maximum of 3 hours while laying down. At the end of the study period the subject will receive an ultrasound scan of the deep venous system of the thigh/groin region to measure hemodynamics at a venous valve during immobility and during use of the OsciPulse device. Finally, the subject will participate in a questionnaire evaluation of their comfort and experience with the OsciPulse device. Participants will be compensated at \$50/ hour for their participation.

Part 2: After informed consent is obtained, baseline demographic and clinical data will be collected. The subjects will be randomized with equal allocation to either of the two treatment sequence groups:

- Group A (OsciPulse device then standard IPC device)
- Group B (standard IPC device then OsciPulse device)

For group A, the OsciPulse device will be applied to the subject on both legs in the first 3 hours. The subject will wear the device for the maximum number of hours as possible up to 3 hours. The [REDACTED] research team inquire with the subject if the device was removed during the testing period.. During the 3-hour period the study team will monitor for adverse events and a hemodynamic ultrasonography may be performed (when feasible) following the Ultrasound SOP. After 3 hours, the subject will complete the questionnaire evaluating the tolerability and safety of the device. In the following 3 hours, the standard IPC will be applied. Subjects will undergo the same procedure for compliance monitoring, adverse event monitoring, hemodynamic ultrasonography (when feasible), and questionnaire evaluation.

For group B, the same procedure will be performed but with the standard IPC in the first 3 hours and the OsciPulse device in the next 3 hours.

Participants will be compensated \$100 for their participation.

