5.4 Duration of Study Participation

Part 1: The duration of study participation will continue for a maximum of 3 hours.

Part 2: The duration of study participation will continue for 6 consecutive hours.

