5.5 Total Number of Subjects and Sites

Part 1: Recruitment will end after 3 subjects have been enrolled.

Part 2: Recruitment will end when no fewer than fifteen (15) evaluable subjects and no greater than twenty (20) evaluable subjects have completed the clinical protocol. In the event a subject begins the clinical protocol, however, does not meet protocol defined requirements of "evaluable" status (see section 9.2, Part 2), the Sponsor reserves the right to replace that subject, which may result in greater than twenty (20) subjects being enrolled. In the unlikely event a disproportionate number of enrolled subjects do not meet the protocol defined requirements for reaching "evaluable" status, the Sponsor may pause the study to enrollment to reevaluate recruitment, inclusion and/or exclusion, or any other activity deemed necessary at the time.

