7.3.3 Part 2 Hour 3(+-1)-6

- Application of IPC device (Group A) or OsciPulse device (Group B)
- Hemodynamic ultrasonography (when feasible)
- Questionnaire assessment at the end of 6 hours
- Adverse Events

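### Part 2 randomizes device order in a two-period crossover, but the paired t-test ignores period: precision is lost if ratings drift, and the estimate shifts if the analysed sequences are unequal

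*Combined protocol and SAP*

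**What the plan says.** Section 4.2.2 sets up the crossover: "The subjects will be randomized with equal allocation to either of the two treatment sequence groups", group A taking OsciPulse first and group B the standard IPC first. The periods follow one another directly (for group A, "In the following 3 hours, the standard IPC will be applied"), and section 5.4 states "The duration of study participation will continue for 6 consecutive hours". The first device is rated at 3 hours. Section 7.3.3 places the second rating at the end of the session: "Questionnaire assessment at the end of 6 hours".

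The analysis does not use the sequence. Section 9.2.4 prescribes "paired t-tests to evaluate the difference between the standard of care cleared intermittent pneumatic device and the OsciPulse device". Sections 9.2.1 (VAS ratings), 9.2.2 and 9.2.6 (hemodynamics) name the same test. For compliance and hemodynamics, section 1 says that "a paired t test will be used to compare those values". Sequence is randomized and recorded (section 4.4) but appears in no analysis.

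On numbers, section 9.2.3 allows for 6 losses among 20 enrolled. Section 5.5 says "Recruitment will end when no fewer than fifteen (15) evaluable subjects and no greater than twenty (20) evaluable subjects" have completed, and permits replacements. Section 9.3 analyses completers only.

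**The concern.** Randomizing the order keeps a period effect from being confounded with the device on average. The analysis must still use the order to keep that effect out of the error term. In a plain paired test, any general change between periods pushes the OsciPulse-minus-IPC difference one way in group A and the other way in group B. The resulting spread counts as noise even under perfect balance. When the sequences are unequal, part of the change also enters the estimate.

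The periods are not obviously exchangeable. The VAS covers comfort, noise, and interference with sleep and movement (section 8.6), in inpatients with reduced mobility. The second period follows 3 hours of wearing the other device. Time in bed, time of day and growing familiarity with a calf cuff or with the scale could each move ratings. These sources are plausible, but the protocol documents none of them.

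At stake is the precision of the primary comparison in a small convenience sample. A wider error term is not a safe default here, because section 4.1 says: "Our hypothesis is that the safety and tolerability of the OsciPulse device is equivalent to the standard compression device". Extra noise makes a non-significant difference easier to obtain and an equivalence interval harder to meet.

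**Working it through.** **Inputs from the protocol.** Two sequences, 1:1, in five blocks of four, so 20 subjects (section 4.4). Section 9.2.3's evaluable number reproduces: 20 − 6 = 14. Section 5.5 requires 15 to 20 evaluable. No SD, period effect, target difference, margin or power is given.

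**Assumptions.** SD of within-subject differences within a sequence s = 20 mm (15 and 30 also tried); period effect p (period 2 minus period 1, same device) from 0 to 15 mm; true difference D = 15 mm; two-sided 5% level; no carryover.

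**Model.** Let d = OsciPulse − IPC. Its mean is D − p in group A and D + p in group B.

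- Paired test (n − 1 df): the expected estimate is D + p(nB − nA)/n, and the expected variance of d is s² + 4p²·nA·nB/[n(n − 1)].
- Period-adjusted: the estimate is (mean of A + mean of B)/2, with expectation [(D − p) + (D + p)]/2 = D and standard error (s/2)√(1/nA + 1/nB), on n − 2 df.

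**One case by hand (7/7, p = 10).** The paired variance is 400 + 4·100·49/(14·13) = 507.7, which is 27% above 400. The 95% half-width is 2.160·√(507.7/14) = 13.0 mm. The adjusted half-width is 2.179·10·√(2/7) = 11.6 mm. The paired interval is about 12% wider.

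**Simulation at 7/7, s = 20, D = 15** (type I error at D = 0). Half-widths are means over runs, so they fall slightly below the hand figures.

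| p (mm) | Power, paired | Power, adjusted | Half-width, paired (mm) | Half-width, adjusted (mm) | Type I error, paired |
|---|---|---|---|---|---|
| 0 | 74% | 73% | 11.3 | 11.4 | 0.050 |
| 3 | 73% | 73% | 11.5 | 11.4 | 0.046 |
| 5 | 71% | 73% | 11.7 | 11.4 | 0.045 |
| 10 | 65% | 73% | 12.8 | 11.4 | 0.030 |
| 15 | 54% | 73% | 14.4 | 11.4 | 0.015 |

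Adjusted type I error stays near 0.05 throughout. With equal sequences the two intervals break even at p ≈ 0.13s for n = 14 (about 2.5 mm) and 0.08s for n = 20 (about 1.7 mm).

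**Other settings at p = 10, power paired vs adjusted.**

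- 7/7: 85% vs 93% at s = 15; 37% vs 41% at s = 30.
- 10/10, s = 20: 83% vs 89%.
- 15 subjects, s = 20: 64% vs 76% if A has 8; 73% vs 77% if B has 8. The gap depends on which way the shift points.

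**Shift of the paired estimate at p = 10.** Zero at equal sequences; 10·1/15 = 0.7 mm at 8/7; 10·2/14 = 1.4 mm at 8/6; 10·4/14 = 2.9 mm at 9/5.

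**How likely is imbalance?** If 6 of 20 (10/10) are lost at random, the hypergeometric probabilities are 37% for 7/7, 49% for 8/6, 13% for 9/5 and 1% for 10/4. The split is therefore unequal 63% of the time. Fifteen subjects cannot split evenly; random loss to 15 gives 8/7 in 70%.

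**Equivalence, illustrated.** With an assumed margin of ±15 mm, D = 0 and 7/7, the chance that the 90% interval lies inside the margin is 69% vs 68% at p = 0, 57% vs 68% at p = 10, and 43% vs 68% at p = 15.

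**The case against.** The best defence is that the paired test remains serviceable. Blocked 1:1 allocation balances period effects by design, and under random loss the bias averages zero. Averaged over random loss to 14, the type I error never exceeds its nominal level (0.050 at p = 0, 0.024 at p = 15). With equal sequences the two point estimates are identical. Over the same losses, the root mean squared error, paired vs adjusted, is 5.36 vs 5.41 mm at p = 3, 5.40 vs 5.41 at p = 5, and 5.55 vs 5.41 at p = 10. All of this stands. The cost is chiefly a wider interval and less power, and it is trivial for a small period effect.

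A second objection also has force. If the second device is rated by contrast with the first, the shift depends on which device came first. A symmetric contrast moves d equally in both sequences. It then acts like carryover rather than an additive period effect, and the adjustment does not remove it. Rating order alone therefore does not establish p; the case rests on general drift over the session.

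The schedule's 3(+/-1) hour start for the second period does not prove unequal period lengths, since section 9.2 defines evaluable subjects as having 3 hours on each device. For hemodynamic change scores, the at-rest reading in section 8.5 may absorb some drift. The plan contains no formal equivalence test or margin, so the equivalence figures are only illustrative.

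None of this supplies a reason to discard the randomized sequence. The objections limit the size of the problem but leave the algebra intact.

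**Conclusion.** The concern holds. The plan randomizes sequence and then leaves it out of every comparison, so any additive period effect inflates the error term and, with unequal sequences, displaces the estimate by p(nB − nA)/n. Under the assumed SD of 20 mm the harm is negligible up to about 3 to 5 mm and moderate from 10 mm: about 8 points of power and a 12% wider interval at 7/7. Any shift depends on the realised split and is usually small. The size rests on assumed values for SD, period effect and true difference; the direction does not. The case is strongest for the VAS ratings. This should be corrected, but it does not invalidate the study.

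**What to change.** Replace the test in section 9.2.4, and align sections 1, 9.2.1, 9.2.2 and 9.2.6, with wording such as:

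> For each outcome measured in both periods (the four VAS ratings, compliance, hemodynamic parameters), the OsciPulse minus IPC difference is averaged within each randomized sequence. The device effect is the unweighted mean of the two sequence means, with a 95% confidence interval from the pooled within-sequence variance on n − 2 degrees of freedom. Numbers and means are tabulated by sequence and period. No carryover between periods is assumed, and no preliminary test for carryover is made.

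The four direct-comparison questions at 6 hours have no per-period pair; summarize them by sequence and average the two sequence results.

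The cost is wording and a few lines of code, using the sequence already recorded. If there is no period effect, intervals widen by 0.9% at 7/7, 1.0% at 8/7, 1.9% at 8/6 and 5.2% at 9/5. Averaged over random loss to 14, power is then 72% instead of 74%. The adjusted estimate is unbiased only without carryover, which this design cannot verify; the paired t-test needs the same assumption.
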